5. STATISTICAL ANALYSES

5.1 GENERAL CONSIDERATIONS

The clinical cutoff date for the primary analysis is defined by the date of the last randomized participant plus 116 weeks.

In the following sections, for all continuous variables for which descriptive statistics are indicated, the following statistics will be reported: the number of observations, the mean, median, standard deviation, and minimum and maximum. The 25th and 75th percentiles

(Q1 and Q3) will also be reported for selected tables. Descriptive summaries of discrete data will include frequencies expressed in terms of number and percentage of participants.

For clinical endpoints and biomarkers assessments, the baseline is defined as the assessment taken at the baseline visit (Day 1) up to and including the day of first study drug intake. If no assessment is reported at the baseline visit up to the day of first study drug intake, the earliest assessment reported after Day 1 and up to the day of second dose or Day 35, whichever is earlier, will be used as baseline. If no assessment is reported either at baseline visit or up to Day 35, an assessment reported at screening will be used as baseline. Day 35 is the latest timepoint allowed for Week 4 visit as per protocol.

For all other assessments, the baseline is defined as the last available assessment prior to first study drug intake, unless specified otherwise.

For biomarkers (CFS and plasma), values below the lower limit of quantification (LLOQ) will be set to $0.5 \times \text{LLOQ}$, while values above the upper limit of quantification (ULOQ) will be set to ULOQ. A summary table will be provided to summarize the values below LLOQ and above ULOQ for each treatment arm.

The efficacy analyses will be based on the ITT analysis set (see [Table 2](#)) and will compare the active drug arm against the placebo arm with regards to mean change from baseline to Week 116. Two-sided test hypotheses will be defined in the following sections and the type I error level will be 5%. There are two identical Phase III studies, for each respective study the type I error level will be 5%. In order to protect the overall type I error rate (i.e., at each study level) when incorporating the hypothesis testing of multiple endpoints into the analysis, a fixed sequence testing procedure ([Westfall and Krishen 2001](#)) will be used to adjust for multiple comparisons. Testing of each hypothesis will follow a pre-specified order such that an endpoint would only be tested if the preceding one in the hierarchy was significant at 5% alpha level. The endpoint hierarchy, starting with the primary endpoint and including only confirmatory secondary endpoints, is the following:

1. CDR-SB (Clinical Dementia Rating, Sum of Boxes)
2. ADAS-Cog 13 (Alzheimer's Disease Assessment Scale, Cognitive subscale, 13-item)
3. ADCS-ADL (Alzheimer's Disease Cooperative Study, Activities of Daily Living scale) total score
4. FAQ (Functional Activities Questionnaire)

Missing outcome data will be handled using data imputation aligned with the estimand, see [Section 5.3.3](#) for a detailed description of the analysis strategy.

When using a statistical model with baseline covariate adjustment, missing baseline covariate data other than the baseline outcome measure will be imputed to the overall median value for continuous covariates, or will be imputed to the most frequent category for categorical variables. In addition, baseline covariates will be derived from information collected into the eCRF, unless otherwise specified.

In statistical models using change from baseline of a given outcome measure as the dependent variable, there will be no imputation of the baseline outcome value, with the consequence that participants missing the baseline outcome measure will not contribute to the analysis.

The impact of the COVID-19 pandemic on the study and its conduct will be monitored and the overall impact will be assessed and described in the Clinical Study Reports.

5.2 PARTICIPANT DISPOSITION

The analysis of participant disposition will be based on all enrolled participants (see Analysis sets in [Table 2](#)). The number of participants enrolled will be tabulated by country, site, and treatment arm. Participant disposition (the number of participants randomized and completing the different study periods) will be tabulated by treatment arm. Premature study drug discontinuation and study discontinuation, as well as reasons for discontinuations, will be summarized.

Major protocol deviations, including major deviations with regard to the inclusion and exclusion criteria, will be summarized by treatment arm. Separate tables will be provided for COVID-19-related major protocol deviations and reasons for COVID-19-related major protocol deviations.

5.3 ENDPOINT ANALYSIS

5.3.1 Definition of Primary Endpoint

As detailed in the study protocols, the primary endpoint is the change from baseline to Week 116 in the CDR-SB which is a global scale covering both functional and cognitive domains.

The CDR-SB is a detailed quantitative general index that is scored from 0 to 18 with higher scores indicating greater impairment. The CDR characterizes six domains: memory, orientation, judgment and problem solving, community affairs, home and hobbies, and personal care. The necessary information to make each rating is obtained through a semi-structured interview with the patient and a reliable informant or collateral source (e.g., a study partner).

5.3.2 Definition of Primary Estimand

The clinical question of interest is to assess the effect of the active drug on disease progression at Week 116, irrespective of use or initiation of symptomatic treatments for AD, in the absence of a substantial impact of the COVID-19 pandemic.

In alignment with the Addendum to [ICH E9](#), the primary efficacy estimand is described by the following attributes:

- **Target Population:**
Early (prodromal to mild) AD population as identified by the inclusion and exclusion criteria, see Sections 4.1.1 and 4.1.2 of the study protocols
- **Variable:**
Change from baseline to Week 116 in Clinical Dementia Rating – Sum of Boxes (CDR-SB)
- **Treatment:**
Prescribed study drug including uptitration to the target dose and safety-related dose modifications, irrespective of use or initiation of symptomatic treatment for AD
- **Population-level summary:**
Difference in variable means between treatment arms

Intercurrent events (ICE):

The ICEs are classified into two categories: those that are Study Drug or Condition Related (SDCR) and those that are not (NSDCR). The list of main anticipated ICEs, and their classification as SDCR or NSDCR, is presented below ([Table 3](#)). The final list of ICEs may need to be adapted in case unanticipated ICEs emerge during the study conduct. The classification of each ICE into SDCR or NSDCR will be completed and documented prior to the unblinding.

The ICE of substantial reduction in drug exposure due to the COVID-19 pandemic is defined as 4 or more dose-months (i.e., 16 weeks, not necessarily consecutive) of treatment missed due to COVID-19-related reasons. This definition will be equally applied to placebo and active arms. One dose-month is defined as 4 weeks of dosing, i.e., one dose with a Q4W dosing frequency (mostly during uptitration) or two doses with a Q2W dosing frequency (at target dose). The threshold of four missed dose-months was determined based on the following reasons:

- A 12-week extension to the study was implemented (in protocol amendment version 4) to mitigate the impact of the COVID-19 pandemic. Therefore, treatment interruptions up to 3 dose-months (i.e., 12 weeks) are already accounted for in the study design.
- Based on the half-life of approximately 24 days of gantenerumab, plasma concentration after a 4 months' interruption at the target dose is expected to be below the observed concentration with the dose of 225 mg Q4W which was

shown to be ineffective in Studies WN25203 (SCarlet RoAD) and WN28745 (Marguerite RoAD).

- A 20% difference is the usual acceptability threshold to establish PK bioequivalence. The protocol includes 20 dose-months (80 weeks) at target dose after the up-titration period. Missing less than 4 dose-months results in an overall reduction in drug exposure of less than 20% of the total planned dose.

As a conservative approach, all withdrawals from study treatment due to an AE will be classified as SDCR for the purpose of the primary analysis. This includes withdrawal from study treatment due to suspected or confirmed COVID-19 infection AE, because the relationship of these events to the participant condition may be ambiguous.

All SDCR ICEs will be handled with a treatment policy strategy, while NSDCR ICEs will be handled with a hypothetical strategy. The frequencies of ICE will be summarized by treatment arm.

In this study, given the disease stage at baseline of the target population, death is expected to be a rare event and mostly not considered related to treatment or disease progression, and as such the corresponding ICE of death will be handled with a hypothetical strategy for the primary estimand. Of note, a supplementary estimand which defines all ICEs, including death, as SDCR (and thus using the same imputation strategy as for the other SDCR ICEs; see Section 5.3.3), is described in Section 5.3.5.

Table 3 Intercurrent Events Impacting Primary Analysis

| Intercurrent Event | SDCR/NSDCR | Estimand Approach |
|--|------------|-----------------------|
| Withdrawal from study treatment due to lack of efficacy | SDCR | Treatment Policy |
| Withdrawal from study treatment due to safety or tolerability reason (NOTE: This will include discontinuation due to AE, incl. suspected or confirmed COVID-19 AEs) | SDCR | Treatment Policy |
| Withdrawal from study treatment with no informative reason given | SDCR | Treatment Policy |
| Withdrawal from study treatment due to the COVID-19 pandemic | NSDCR | Hypothetical Strategy |
| Substantial reduction in drug exposure due to the COVID-19 pandemic (defined as ≥ 4 missed dose-months) | NSDCR | Hypothetical Strategy |
| Withdrawal from study treatment due to purely administrative reason | NSDCR | Hypothetical Strategy |
| Death | NSDCR | Hypothetical Strategy |
| Withdrawal from study treatment due to use or initiation of protocol prohibited medication | SDCR | Treatment Policy |
| Withdrawal from study treatment due to other SDCR ICEs | SDCR | Treatment Policy |

AE = adverse event; COVID-19 = coronavirus disease 2019; NSDCR = Non Study Drug or Condition Related; SDCR = Study Drug or Condition Related

ICE Derivation

Identification and categorization of the ICEs will be done based on fully blinded data only and will be finalized before database lock.

The number of missed dose-months due to the COVID-19 pandemic will be derived from the standardized eCRF data fields. More specifically, any Q4W missed dose due to COVID will count as 1 missed dose-months, while any Q2W missed dose due to COVID will count as 0.5 missed dose-months. The information whether a dose was missed due to COVID will be derived from the corresponding “reason for missed visit” and “reason for missed dose” fields in the eCRF.

All occurrences of “withdrawal from study treatment” ICE, as per [Table 3](#), will be identified and categorized as SDCR/NSDCR based on the standardized reason reported in the eCRF “Study Drug Completion/Early Discontinuation” form. In case of ambiguity (i.e., if the reason for study drug discontinuation as reported in the eCRF is either “Protocol deviation”, “Withdrawal by subject”, “Physician decision” or “Other”), an adjudication committee will review the dedicated eCRF free text field and assign the withdrawal to a pre-specified ICE and a corresponding SDCR or NSDCR category. The

adjudication committee may also introduce additional ICES to the list, in case where no appropriate fit is found in [Table 3](#) or [Appendix 2](#). The adjudication committee members must not have been involved in the conduct of Studies GRADUATE I and GRADUATE II and must not have been exposed to unblinding data from these studies. The members of the adjudication committee must have signed the charter of the adjudication committee, in [Appendix 3](#).

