### **4.7 TREATMENT, PARTICIPANT, STUDY, AND SITE DISCONTINUATION**

#### **4.7.1 Study Treatment Discontinuation**

Participants must discontinue study treatment if they experience any of the following:

- Any medical condition that the investigator or Sponsor determines may jeopardize the participant's safety if he or she continues to receive study treatment
- Investigator or Sponsor determines it is in the best interest of the participant
- Pregnancy
- Upon evidence of more than 15 ARIA-H, cumulatively
- Any disseminated leptomeningeal hemosiderosis

All participants who withdraw from treatment will be asked to return 2 weeks after last dose in order to complete the early termination visit assessments.

In addition, participants who withdraw from treatment will be asked to return for collection of safety (except MRI) and limited efficacy data (i.e., the primary and secondary endpoints) at visits that have efficacy assessments according to the schedule of activities until the end of the double-blind treatment period, *and then the follow-up visits*, or until the last OLE follow-up visit (OLE Follow Up 2) for those who enrolled in the OLE.

The primary reason for study treatment discontinuation should be documented on the appropriate eCRF. Participants who discontinue study treatment prematurely will not be replaced.

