- If the onset date is missing, and the end date is on or after the first dosing date or unresolved or missing, then the event will be considered to have started after the first dose of study drug.

The following data handling rules will also be applied for specific tables:

- An AE will be included in the summary table of AEs leading to study drug discontinuation if the “action taken with blinded gantenerumab” drop-down menu on the AE eCRF is checked “drug withdrawn”.
- In the summary table of AEs by intensity, if a participant has more than one occurrence of an event, the event with the most severe intensity will be counted. If the intensity of an AE is missing, then the AE will be included only in the total number of events column, and not in the count of participants with the event by intensity.
- In the summary table of AEs related to study drug, if a participant has more than one occurrence of an event, the related event will be counted if applicable. If the relationship of an AE is missing, then the AE will not be included.

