5.2 SCHEDULED MEETINGS

The number of meetings will depend on the amount of data to be reviewed by the ACI. The Study Team and the ACI will agree on the number of meetings to be held during the organizational meeting.

The Study Team will prepare reports including data to be reviewed. These reports will be provided to the ACI at least three business days prior to each meeting ([Appendix 1](#)). The content of these reports is limited to eCRF data extracted from:

- “Study Drug Completion/Early Discontinuation” form including :
 - “Completion/discontinuation reason” item
 - Free text field " If primary reason is protocol deviation, withdrawal by subject, physician decision or other, specify"

The data will be extracted from the eCRF and provided in a tabular format to the committee. ACI meetings will not be attended by the GRADUATE Study Team.

For ACI meetings to take place all three members should be attending. The decisions should be made in a unanimous way. However if this is not possible in some cases, the Chair has the casting vote.

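### The SAP counts every AE-driven treatment withdrawal as SDCR, but its derivation reads only the discontinuation form, so a few such withdrawals could be classed NSDCR

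*SAP*

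**What the plan says.** SAP 5.3.2 (Definition of Primary Estimand) describes a conservative rule: "all withdrawals from study treatment due to an AE will be classified as SDCR for the purpose of the primary analysis". It extends this to withdrawals for suspected or confirmed COVID-19 infection reported as an AE. Table 3 separately classes withdrawal because of the pandemic, and withdrawal for purely administrative reasons, as NSDCR.

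Under ICE Derivation in the same section, withdrawals from treatment "will be identified and categorized as SDCR/NSDCR based on the standardized reason reported in the eCRF" on the study drug completion/early discontinuation form. Four recorded reasons count as ambiguous: protocol deviation, withdrawal by subject, physician decision and other. For these, "an adjudication committee will review the dedicated eCRF free text field and assign the withdrawal to a pre-specified ICE" and an SDCR or NSDCR category. Appendix 3, section 5.2, describes what the committee receives: "The content of these reports is limited to eCRF data extracted from" that same form, namely its reason item and its free text.

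The safety analysis uses another source. In SAP 5.6.2, "An AE will be included in the summary table of AEs leading to study drug discontinuation if the" action-taken "drop-down menu on the AE eCRF is checked" as drug withdrawn.

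Two other provisions bear on the point. Protocol 4.7.1 asks for a single reason: "The primary reason for study treatment discontinuation should be documented on the appropriate eCRF". Table 3 also has a default row, "Withdrawal from study treatment with no informative reason given", which is SDCR.

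**The concern.** The rule is written in terms of why the participant stopped, and the derivation in terms of which box was ticked on one form. The two can differ. A participant may have an AE for which the site recorded drug withdrawn, while the single primary reason on the discontinuation form is withdrawal by subject, with free text about the pandemic or an administrative matter. COVID-19 is the clearest case. Brief free text naming COVID-19 does not separate an infection AE (SDCR) from visit disruption (NSDCR), and the committee has no AE record to settle it.

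The label decides how the data are handled (SAP 5.3.3). For an SDCR withdrawal, observed later CDR-SB values are kept, and missing ones are imputed with placebo increments, so no further benefit accrues. For an NSDCR withdrawal, observed later values are discarded and everything after the stop is imputed as if randomised treatment had continued. The same participant could then be an AE discontinuation in the safety table and a hypothetical continuer in the primary analysis.

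More such stops on active drug than on placebo would be plausible. ARIA findings that change study treatment are reported as AEs (Protocol 5.3.5.1), and Protocol 4.7.1 lists ARIA-H criteria for stopping treatment. No rate of ARIA-driven discontinuation is given for this trial.

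**Working it through.** **1. Rule against sources.**

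| Item | Source read |
|---|---|
| SDCR rule for AE withdrawals (5.3.2) | None named |
| ICE category, unambiguous reason (5.3.2) | Discontinuation form, reason item |
| ICE category, ambiguous reason (5.3.2; Appendix 3, 5.2) | Discontinuation form, reason item and free text |
| AEs leading to discontinuation (5.6.2) | AE form, action taken |

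Nothing in the SAP or the charter makes the ICE derivation read the AE action field, or requires the two forms to agree.

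**2. Who can be misclassified.** Three things must coincide: an AE with action drug withdrawn; a different primary reason on the discontinuation form; and a reason or free text that points to an informative pandemic or purely administrative cause. A bare subject decision falls under the no-informative-reason row and is SDCR.

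**3. Size per participant.** Inputs: the Appendix 1 mean trajectory (1 point of decline over the first 52 weeks, then 1.5 points per year) and the 30% slowing of SAP Section 3, applied here at every visit as an assumption. Check against the plan: the placebo change at Week 104 is 1 + 1.5 × 52/52 = 2.5, the figure in Section 3.

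Treatment effect at week w = 0.30 × placebo change. For a stop with no later data, NSDCR handling credits the full Week 116 effect, while SDCR handling credits only the effect reached at the last on-treatment visit. The difference is effect(116) − effect(w), computed from unrounded values.

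| Week | Placebo change | Effect | Added benefit if labelled NSDCR |
|---|---|---|---|
| 24 | 24/52 = 0.462 | 0.138 | 0.715 |
| 52 | 1.000 | 0.300 | 0.554 |
| 76 | 1 + 1.5 × 24/52 = 1.692 | 0.508 | 0.346 |
| 116 | 1 + 1.5 × 64/52 = 2.846 | 0.854 | – |

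**4. Size in the estimate.** Shift = affected share of the active arm × added benefit.

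- 1% affected: 0.01 × 0.346 to 0.01 × 0.715 = 0.0035 to 0.007 points.
- 5% affected (about 25 of 508): 0.05 × 0.346 to 0.05 × 0.715 = 0.017 to 0.036 points, or 2% to 4% of 0.854.

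For scale, the unadjusted standard error on the plan's SD of 2.97 with 508 per arm is 2.97 × √(2/508) = 0.186. The 5% case is 9% to 19% of one standard error.

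**5. Cross-check by simulation.** This used the Appendix 1 means, variances, correlations and SDCR model, with a 30% slower decline on active, errors in the active arm only, no NSDCR events, and all later data missing for the misclassified. Between 15% and 25% of the active arm then had an SDCR event, with a mean added benefit of 0.45 to 0.47. Moving 15% of those events to NSDCR shifts the estimate by 0.010 to 0.017 points; moving 45% shifts it by 0.031 to 0.051. With the highest active-arm SDCR frequency in Appendix 1 (33%), 15% misclassified gives 0.33 × 0.15 × 0.466 = 0.023, inside the 5% range of step 4.

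**6. What Appendix 1 already covers.** It moves 0% to 45% of SDCR events to NSDCR and reports type I error of 4.69% to 5.18%. The stated Monte Carlo error reproduces: √(0.05 × 0.95/10,000) = 0.22%. Every run is under the null, and the misclassification rate is not varied by arm.

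**The case against.** Much of the case against this point stands.

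- **Default.** A reader might infer that the SDCR default protects only empty text fields. Table 3 says otherwise: it covers any uninformative reason. The administrative category also requires a purely administrative reason, so text that mixes an AE with logistics does not fit it.
- **Direction.** A reader might infer that each such error favours gantenerumab. The calculation shows that only for a beneficial drug and missing later data. With no effect the expected shift is about zero, and with harm it reverses. Where later values were observed, which SAP 1.2 urges sites to collect, the sign depends on those values.
- **Imbalance.** Injection reactions are weak support: Protocol 1.2.3 reports two discontinuations (0.3%) in WN25203 and none in WN28745. ARIA is the better argument, but the protocol says most ARIA did not require permanent cessation.
- **Data cleaning.** Protocol 7.1 provides for queries on discrepant data, and the charter places adjudication after cleaning and medical data review. Some cases may be caught there. Neither passage specifies this cross-check, and the EDC specification that might do so is not among the documents.
- **Supplementary analysis.** The treatment-policy estimand in SAP 5.3.5.2 handles all ICEs alike, so the label has no effect on it. It does not correct the primary estimate, and it also changes the handling of genuine pandemic ICEs, so it does not isolate this error.

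**Conclusion.** The point holds, and it is minor. The derivation as written cannot guarantee the SAP's statement that all AE withdrawals are SDCR, and an informative pandemic or purely administrative entry on the discontinuation form is the way through.

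The likely effect is small: 0.0035 to 0.007 points at 1% of the active arm and 0.017 to 0.036 at 5%. These figures rest on the Appendix 1 trajectory, an assumed 30% slowing, stops after Weeks 24 to 76 and missing data afterwards. The 1% and 5% shares are illustrations; the documents give no basis for either.

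A reader might go further and infer that type I error is compromised. The documents do not support that: the SAP's simulations of misclassification in this direction stay near 5%. What they leave open is bias in the estimate when the drug works and errors differ by arm.

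**What to change.** Add to ICE Derivation in SAP 5.3.2: before the blinded ICE categories are finalised, any withdrawal-from-treatment ICE in a participant who has at least one AE with action taken recorded as drug withdrawn is classified SDCR, whatever reason the discontinuation form gives. State that the Death category in Table 3 and the first-ICE rule in 5.3.3 are unchanged. Otherwise a fatal AE marked drug withdrawn would be moved by accident.

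Add the AE action field to the committee's listing in Appendix 3, section 5.2. Only the flag is needed, not the AE term, and it does not identify treatment assignment. After unblinding, report the number of discordant cases by arm, so that readers can see whether the gap mattered.

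The cost is one SAP sentence, one charter line and a blinded cross-check of two existing forms. The primary estimate may come out slightly less favourable.
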